# 1.0 Objectives and Endpoints

### **1.1 Primary Objectives:**

• To determine whether glutamine decreases the severity of mucositis in patients on an mTOR inhibitor-based regimen or esophagitis in patients receiving radiation to the esophagus.

### 1.2 Secondary Objectives:

- To assess whether glutamine regimen improves quality of life (QOL) in patients during mTOR inhibitor containing regimen and esophagitis during radiation to esophagus.
- To assess whether glutamine improves other measures of mucositis/esophagitis including incidence of any mucositis/esophagitis, incidence of grade 3 or higher mucositis/esophagitis, duration of mucositis/esophagitis, delay in onset of mucositis/esophagitis, and interruption of cancer treatment due to mucositis/esophagitis.
- To assess whether glutamine affects weight loss after six months of treatment for mTOR inhibitor patients and after completion of radiation therapy for esophagus radiation patients.
- To assess toxicity profile of glutamine.
- To assess whether glutamine affects muscle breakdown.

# 2.0 Background

# 2.1 Introduction

# 2.1.1 mTOR Inhibitors and Mucositis

Temsirolimus (Torisel; Wyeth Pharmaceuticals, PA) is a mammalian target of rapamycin (mTOR) inhibitor that gained FDA approval in 2007 for the treatment of advanced renal cell carcinoma. Another mTOR inhibitor, everolimus, has been approved for renal cell carcinoma, breast cancer, and neuroendocrine tumors. In addition, mTOR inhibitors have demonstrated encouraging efficacy results in patients with a range of advanced malignancies, alone or in combination with other chemotherapy agents or targeted therapies in trials for multiple forms of malignancies. As a central regulator of key pathways important in the proliferation of cancers, the mTOR inhibitor blocks the aberrant activation of phosphoinositide 3-kinase (PI3K)/Akt signaling pathway, resulting in growth arrest of cancer cells halting in the G1 phase of the cell cycle.

In general, mucositis is among the most common side effects reported from mTOR inhibitor-based treatment, which seems to be dose-related and occurs mostly in earlier cycles. It has been identified repeatedly as one of the most common dose-limiting toxicities. The mucositis incidence related to temsirolimus treatment as a single

agent was 41% in patients with solid tumors with 3% of grade 3 or above. However, 2 recent reviews of temsirolimus-based treatment demonstrated that the mucositis incidence rate ranged from 60-65% with 5-10% of patients developing Grade 3. The treatment that Investigational Cancer Therapeutics generally uses for the management of mucositis uses the following: xyloxylin (1:1:1 ratio of diphenhydramine, Maalox, lidocaine; 10 milliliters (mL) swish/ swallow every 6 hours as needed). This treatment is not used prophylactically, but used when patient develops mucositis. There is no standard mucositis treatment; therefore, it is important to improve mucositis treatment for patients on therapy with mTOR inhibitors.

# 2.1.2 Radiation and Esophagitis

More than 1.5 million new cases of cancer are expected to occur in the United States in 2010, including more than 200,000 new cases of lung cancer and 16,000 new cases of esophageal cancer. The primary aim of thoracic radiotherapy (TRT) in both NSCLC and esophageal cancer is to maximize the therapeutic ratio in order to deliver an effective dose to the tumor while maintaining an acceptable dose to the neighboring normal tissues. However, complications such as acute radiation-induced esophagitis (ARIE) may cause significant morbidity, unplanned treatment delays, and a decreased chance to escalate the dose to more effective levels. These issues may reduce tumor control and survival rates, as well as the patients' quality of life (QOL).

ARIE is often the dose-limiting complication that is reported in 5–100% of patients treated with TRT. Clinical and dosimetric factors that may be related to the incidence and severity of ARIE include: age, tumor and nodal stage, concurrent chemoirradiation, mean esophageal dose and maximal dose point, and esophageal volume receiving >35 Gray (Gy) (V35), V45, V50, V60, percent length of esophagus receiving >40 Gy, and >66 Gy full circumferences. Most of these factors are closely associated with the total radiation dose received by a certain volume of esophagus. Thus, to prevent ARIE, the dose to the esophagus must be kept under the organ tolerance level, which can possibly be achieved by complete exclusion of the esophagus from the RT field by using novel RT techniques, such as intensity modulated RT (IMRT). However, often this approach is not feasible due to the organ's central position in the mediastinum, and the proximity of involved lymph nodes relative to the esophagus. Therefore, the primary strategies in controlling ARIE currently revolve around identifying an effective radioprotective agent. Based on the significant prior data, review below (section 2.2 and 3.0) we believe that glutamine will prove to be a safe and effective radioprotector of the esophagus.

The rate of grade three esophagitis ranges between 15-30% in modern studies. The rate seen in most recent NSCLC trial using concurrent chemo/radiation at MD Anderson was 16%. This compares favorable compared to the historic rates of other institutions such as the CALGB 9781 which has a 27% rate. For patients developing Grade 3 esophagitis, radiotherapy can be continued with pain management and IV support, or radiotherapy can be held for </= 5 days until symptoms are < Grade 3.

# 2.2 Rationale

# 2.2.1 Rationale in mTOR Treatment Patients

Anti-cancer agents damage cells in the intestine and oropharynx, which leads to mucositis. Mucositis induced by anti-cancer treatment may be the result of multiple factors. Anti-cancer agents inhibit the DNA synthesis of rapidly proliferating cells in the mucosa, and it hinders the renewal capacity of basal epithelium. Subsequently, that results in mucosal atrophy and collagen breakdown thus leading to ulceration.

Mucositis is a notable side effect and dose-limiting toxicity for patients in mTORbased regimens. Mucositis is further associated with dehydration and weight loss among patients undergoing temsirolimus-based trials. In a recent study, mucositis was noted to be the most frequent adverse event overall (73.4%) among 2,822 patients who received a temsirolimus-based, everolimus-based, or ridaforolimusbased regimens. In a study of single-agent temsirolimus treatment in patients with advanced renal cell carcinoma, mucositis was 41.3%.

In a recent data review, we assessed the incidence and severity of mucositis in 87 patients who received one of 3 temsirolimus-based combination trials. Overall, the incidence of any grade of mucositis in our temsirolimus-based combination trials was 64.4%. The incidence rate of mucositis greater than grade 2 was higher at 9.2%. We also examined the effectiveness of our mucositis management, which included one or more of the following: xyloxylin (1:1:1 ratio of diphenhydramine, Maalox, lidocaine; 10 milliliters (mL) swish/ swallow every 6 hours as needed), Caphosol (sodium phosphate; 15 mL swish/spit every 4 hours as needed), valacyclovir (500 mg *per os* 3 times daily), Biotene mouth wash (every 4 hours as needed), and Carafate (1 gram (gm)/ 10 mL; 10 mL swish/swallow or spit every 6 hours as needed) as previously described by Naing *et al.*, 2011. However, there was no standard protocol to treat mucositis. Based on physician discretion, there were some patients who received one or more of our mucositis regimens.

A better regimen for mucositis is indeed warranted. Although not utilized in our 3 trials, oral glutamine may be a promising regimen for mucositis treatment. Use of oral glutamine during and after the anti-cancer treatment has been shown to reduce the duration and severity of mucositis.

In mTOR based combination therapy, mucositis is a major obstacle. By optimizing treatment for mucositis through the use of glutamine, it will enable patients to continue to have an effective treatment while maintaining good quality of life. Hence, it is of great importance to devise an optimal regimen in both prophylactic and treatment settings. The primary objective of the current study is to prospectively demonstrate that oral glutamine use decreases the severity of mucositis in patients receiving mTOR-based therapy.

# 2.2.2 Rationale in Radiation Treatment Patients

An agent with potential radioprotective properties is glutamine, which is the primary oxidative fuel of the gut epithelium and is necessary for maintenance of the integrity of the gut structure during normal and stress conditions. Significant amounts of glutamine are provided by skeletal muscles during hypercatabolic states such as cancer, however marked glutamine depletion develops over time, which cannot be compensated for by increased synthesis. Glutamine depletion under conditions of stress compromises the acid–base balance, immune functions, epithelial integrity, and facilitated bacterial translocation in the gut. Furthermore, because of its protective functions against oxidative injury in normal tissues, depletion of glutathione (GSH), a byproduct of glutamine metabolism, may increase the extent of tissue damage caused by RT and/or chemotherapy (Ctx). In this setting, glutamine supplementation not only normalizes the levels in the body, but also selectively increases normal tissue GSH levels, which may explain its selective radioprotective actions on normal tissues.

In cancer patients, there is a tendency for progressive depletion of glutamine from muscle, which is a key factor in cancer-induced cachexia. As muscle depots are the immediate source of glutamine for gut epithelium, glutamine depletion in such conditions may lead to reduced radiation tolerance. Additionally, ARIE and related complications such as nausea, vomiting, pain, dysphagia, or odynophagia may further worsen the tolerance of normal tissues to radiation. Therefore, it is reasonable to assume that glutamine supplementation may be beneficial in prevention of ARIE and related complications in patients undergoing TRT. This evidence suggests a selective radioprotective role for glutamine, and in the radiology department, we use glutamine in all patients with NSCLC in whom mediastinal irradiation is indicated. The primary objective of the current study is to prospectively demonstrate that oral glutamine use in the prevention of ARIE and weight loss in thoracic cancer patients during TRT.

# 3.0 Background Drug Information

[figure not shown]
### Drug Name: Glutamine + disaccharide suspension (Healios)

**Classification:** Amino Acid, carbohydrates; Generally Recognized As Safe (GRAS) enteral nutrition and flavoring supplement

**Description:** Glutamine, a precursor for glutathione, plays a pivotal role in regulating the intracellular redox potential, and clinical investigations indicate that glutamine inhibits other mediators of mucosal barrier injury by reducing the production of proinflammatory cytokines and cytokine-related apoptosis. Other experimental evidence suggests that glutamine may improve mucosal barrier wound healing by increasing fibroblasts and collagen synthesis. Glutamine is also critically important to meet demands for tissue repair during times of high cellular replication. In these times of increased glutamine demand caused by physiologic stress (e.g., during and after cytotoxic chemotherapy), the requirements for glutamine may

[figure not shown]
exceed the body's ability to produce sufficient concentrations and exogenous glutamine may be needed.

Glutamine suspension in combination with the disaccharide sucrose has vastly improved uptake by mucosal cells (Figure 1). It takes <10 seconds for this effect to be completed.

**Figure 1**. Glutamine transport into cells is facilitated by disaccharides. (from Peterson et al, ASCO plenary session 2008)

Until recently trehalose, a glucose-glucose disaccharide with cell membrane and protein stabilizing properties was expensive. It is now made from starch for mass production and is available as a good tasting sweetener (Treha, Cargill). Figure 2 shows the similar structures of sucrose and trehalose.

**Figure 2.** Sucrose is Glucose + fructose; trehalose is Glucose+Glucose (source: Google images)

Use of a glutamine + disaccharide suspension has been safe and effective in reducing mucositis pain and oral discomfort in 1 pilot study and 3 randomized, placebo double blind clinical trials. Since trehalose is now commercially available, an improved orange-flavored formulation with all three generally recognized as safe components (glutamine, sucrose, trehalose) has been developed by Labrada Nutrition in Houston and given the brand name Healios.

# 3.1 Preparation:

The drug and placebo will be provided by Healios Oncology Nutrition.

**Glutamine (Active):** supplied as a powder. 1 scoop provides the individual serving of 4 grams glutamine (other components include 5 grams (gms) sucrose, 1.3 gm trehalose, 130 mg suspending agent to prevent quick settling, and 0.7 gm flavoring). One scoop is suspended with 25-100 milliliters (mL) water.

**Glycine (Placebo):** supplied as a powder. 1 scoop provides the individual serving of 4 grams glycine (other components include 5 grams (gms) sucrose, 1.3 gm trehalose, 130 mg suspending agent to prevent quick settling, and 0.7 gm flavoring). One scoop is suspended with 25-100 milliliters (mL) water

# 3.2 Method/Route of Administration:

# **Oral Administration**

- **mTOR-based Therapy Cohort:** The suspension is swished for 10 seconds, then swallowed.
- **Espophageal Radiation Patients:** The suspension is swallowed in several small boluses.

# 4.0 Patient Eligibility

# 4.1 Inclusion Criteria

- Patients who will be initiating therapy with any investigator-initiated mTOR inhibitor based therapy in the Department of Investigational Cancer Therapeutics (Phase I Program) or initiating radiation therapy to the esophagus.
- For the esophagitis arm, any patient with thoracic malignancies, which will receive radiation alone or concurrent chemo/radiation. Radiation dose must be ≥ 45 Gy. For the esophagitis arm, induction chemotherapy is allowed.
- Ability to understand and the willingness to sign a written informed consent. A signed informed consent must be obtained prior to any study specific procedures.
- 4) Patients must be >/= 17 years of age.
- 5) Women of child-bearing potential MUST have a negative serum or urine pregnancy test unless prior hysterectomy or menopause (defined as 12 consecutive months without menstrual activity). Patients should not become pregnant or breastfeed while on this study. Sexually active patients must agree to use contraception prior to study entry, for the duration of study participation, and for 30 days after the last dose.

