# 5.1.2 Radiation to the Esophagus

Radiation must be  $\geq$ 45 Gy delivered alone or with concurrent chemotherapy. The type of concurrent chemo will be determined by the treating physician. For the esophagitis arm, induction chemotherapy is allowed. XRT must be given using

conventional daily fraction dose from 180-240 cGy per day. Radiation technique may include: 3D conformal, IMRT, and or protons. Glutamine will start on the first day of radiation, or within 10 days of the start of radiation and will be continued for 4 weeks after the last day of radiation. Radiation will be given daily (Monday through Friday) for 5 days per week. The number of weeks of radiation therapy will be determined by the treating physician. The end of treatment week will vary based on the number of weeks of radiation that the patient receives.

[figure not shown]

Figure 3. Treatment Regimen (Schema)

For patients who will receive mTOR inhibitor based therapy: the patients will be randomized to receive either placebo or Glutamine beginning on Day 1 of an mTOR inhibitor based therapy.

**For patients who will receive radiation to the esophagus:** the patients will be randomized to receive either placebo or Glutamine beginning on Day 1 of radiation treatment, or within 10 days of the start of radiation.

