### 12.5 Randomization and Blinding

Patients will be equally randomized between treatment arms using permuted blocks within strata separately for the two groups of patients. For patients who will receive mTOR inhibitor based therapy, randomization will be stratified by: prior mucositis (Y/N), and prior radiation therapy to the head and neck (Y/N). For patients who will

receive radiation to the esophagus, randomization will be stratified based on the volume of esophagus receiving 40 Gy: (1) 20-40%; (2) 41-60%; (3) 61-80%.

CORe will set up a Randomization website and the Investigational Pharmacy personnel will perform the randomization assignment.

Both patients and the research staff conducting the assessment will be blinded to the treatment assignment. Placebo powder identical to glutamine powder in appearance and taste will be compounded by Healios Nutrition Oncology, and both will be dispensed by Investigational Pharmacy at MD Anderson. At the end of the blinded phase, we will assess blinding by asking patients which study arm they believe they have been randomized to.

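### The radiation cohort pools radiation alone with concurrent chemoradiation, but the primary Wilcoxon test ignores both chemotherapy and the volume strata, giving up some efficiency and protection against chance imbalance.

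*Combined protocol and SAP*

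**What the plan says.** - **Eligibility (4.1):** the radiation cohort takes "any patient with thoracic malignancies, which will receive radiation alone or concurrent chemo/radiation". Section 5.1.2 adds: "The type of concurrent chemo will be determined by the treating physician".
- **Risk factors (2.1.2):** "Clinical and dosimetric factors that may be related to the incidence and severity of ARIE include: age, tumor and nodal stage, concurrent chemoirradiation". The list goes on to several dose and volume measures.
- **Randomisation (12.5):** "Patients will be equally randomized between treatment arms using permuted blocks within strata separately for the two groups of patients". For the radiation cohort, "randomization will be stratified based on the volume of esophagus receiving 40 Gy", in three bands. Chemotherapy is not a factor.
- **Primary analysis (12.4):** a Wilcoxon rank sum test of ordered severity grades between arms, run separately in each cohort, with no strata or covariates.
- **Sample size (12.3):** 40 per arm in the radiation cohort gives 81% power at two-sided 5%, for control grades 26/37/37% (grades 0-1, 2, 3) against 50/38/12% on glutamine.

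No section plans an adjustment, subgroup or sensitivity analysis by chemotherapy.

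**The concern.** Whether a patient is to have concurrent chemotherapy is part of the treatment intention at entry, so it can be recorded before randomisation. The protocol itself puts it on the list of factors that may bear on the primary endpoint. The plan already balances one such factor, the esophageal volume receiving 40 Gy, but leaves this one to chance and uses neither in the primary test.

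Two things are at stake. First, if chemotherapy affects grade, a test that compares like with like detects the same glutamine effect somewhat more often. Second, with 40 patients per arm, one trial can end with visibly different chemotherapy shares. An adjustment chosen after seeing that imbalance would be post hoc, whereas one written down beforehand would not be open to that criticism.

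**Working it through.** **1. The plan's own power figure (12.3).** The probability that a control patient has a worse grade than a glutamine patient, counting ties as half, is built up as follows.

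- Control worse: 0.37 × 0.50 + 0.37 × (0.50 + 0.38) = 0.511
- Tied: 0.26 × 0.50 + 0.37 × 0.38 + 0.37 × 0.12 = 0.315
- Sum: 0.511 + 0.315/2 = 0.668

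The pooled grade proportions are 0.380, 0.375 and 0.245, and their cubes sum to 0.122. The tie-corrected null variance is 80/(12 × 40 × 40) × (1 − 0.122) = 0.00366, so the SD is 0.0605. Then 0.168/0.0605 − 1.960 = 0.82, which gives 79.4% power. Using a separate variance under the alternative gives 81.1%, and simulation of 200,000 trials gives 81.2%. The stated 81% reproduces.

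**2. Chance imbalance.** Assume 70% of 80 patients (56) have concurrent chemotherapy and the arms are 40/40. The number with chemotherapy in one arm is hypergeometric, with variance 40 × 0.7 × 0.3 × 40/79 = 4.25. The SD of the difference in shares is 2 × √4.25/40 = 0.103. The table gives exact probabilities. They treat chemotherapy as unrelated to the volume strata.

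| Assumed share | ≥10 points | ≥15 points | ≥20 points |
|---|---|---|---|
| 50% | 50% | 26% | 12% |
| 70% | 46% | 22% | 9% |
| 80% | 40% | 16% | 5% |

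**3. What an imbalance does to the grades.** Split the control distribution by chemotherapy under proportional odds, with share 70% and odds ratio 3 for a worse grade. Grade 3 is then 21% with radiation alone and 44% with chemoradiation. A 20-point imbalance moves grade 3 by 0.20 × (0.44 − 0.21) = 0.046, or about 4.6 points, against a planned difference of 37 − 12 = 25 points. On the Wilcoxon scale it moves the probability from 0.500 to 0.531, which is about 0.031/0.168, or just under a fifth of the planned effect.

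**4. Power with and without stratifying the test.** Both overall distributions from 12.3 were split by chemotherapy in the same way, with 100,000 simulated trials per scenario. The plain Wilcoxon was compared with a van Elteren test stratified by chemotherapy. Share and odds ratio are assumptions.

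| Share | Odds ratio | Chemotherapy balanced: plain → stratified | Left to chance: plain → stratified |
|---|---|---|---|
| 50% | 1 | 81.1 → 81.1 | 80.9 → 80.4 |
| 50% | 2 | 81.4 → 82.4 | 80.9 → 81.9 |
| 50% | 3 | 81.9 → 84.4 | 80.9 → 84.0 |
| 50% | 5 | 83.0 → 88.0 | 81.0 → 87.6 |
| 70% | 1 | 81.3 → 81.2 | 81.2 → 80.5 |
| 70% | 2 | 81.4 → 82.2 | 81.0 → 81.8 |
| 70% | 3 | 81.9 → 84.0 | 81.1 → 83.5 |
| 70% | 5 | 82.6 → 86.8 | 81.1 → 86.4 |
| 85% | 1 | 80.9 → 80.8 | 81.2 → 80.5 |
| 85% | 2 | 81.1 → 81.7 | 81.0 → 81.4 |
| 85% | 3 | 81.6 → 82.9 | 81.1 → 82.3 |
| 85% | 5 | 82.0 → 84.3 | 81.0 → 84.1 |

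With chemotherapy balanced between arms, the gain is about 1 point at odds ratio 2, 1-3 at 3 and 2-5 at 5. If randomisation is left as it is, the gain is 0.4-1.0, 1.2-3.1 and 3.1-6.6 points. The cost when chemotherapy has no effect is 0.5-0.7 points.

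**5. Type I error.** With chemotherapy left to chance, both tests stay between 4.8% and 5.1% in every scenario. If chemotherapy is balanced by design but the plain Wilcoxon is kept, the true level at odds ratio 3 falls to 4.0-4.4%. The same mechanism applies to the volume strata already in 12.5 if volume affects grade; its size there was not computed.

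The simulations stratify by chemotherapy only. They do not include the volume bands.

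**The case against.** The strongest reply is that the plan is valid as written. The 81% rests on overall grade distributions, which already average over the patient mix if they fit this population, and randomisation protects the test. Section 2.1.2 also goes on to say that most of the listed factors are tied to the dose received by a volume of esophagus, which supports a dose-volume stratifier. Age and stage are on the same list, and 80 patients cannot be stratified on everything.

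Most of this stands. The volume factor is a sensible choice, and further randomisation strata are a trade-off at this size. But the reply does not cover the analysis. Nothing in the documents says that volume stands in for chemotherapy, and the primary test leaves out even the volume strata.

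Three stronger readings are tempting, and the documents do not support them.

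- **That the trial falls short of 81%.** It does not. The figure reproduces, and the plain test has about 81% power in every scenario with chemotherapy left to chance.
- **That the protocol treats chemotherapy as an established cause of worse esophagitis.** Its wording is that the factors may be related, and it gives no effect size.
- **That the mTOR cohort needs a single-agent versus combination stratum.** The background gives 41% mucositis (3% grade 3 or above) for single-agent temsirolimus and 64.4% (9.2% above grade 2) for combinations. These come from different studies and populations. No single-agent share is given for this cohort, and the mTOR planning data match in number the 87 patients from combination trials in 2.2.1.

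**Conclusion.** The point holds as a modest, cheap improvement to the radiation cohort's primary analysis. It is not an error in the sample size or a threat to validity. A reader might infer from the imbalance figures that the test is biased; it is not, because the imbalance is random and type I error stays near 5%. The loss is efficiency and credibility in a single trial. With chemotherapy balanced, about 1 point of power is forgone at odds ratio 2, 1-3 at 3 and 2-5 at 5, and none if chemotherapy has no effect. A 20-point imbalance occurs in about 9% of trials at a 70% share. These sizes rest on an assumed share of 50-85%, assumed odds ratios and proportional odds for the chemotherapy effect. The direction does not depend on the exact values, provided that chemotherapy affects grade.

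**What to change.** In 12.4, for the radiation cohort, pre-specify the primary comparison as a van Elteren (stratified Wilcoxon) test, or a proportional-odds model, that includes planned concurrent chemotherapy (yes/no) and the existing 40 Gy volume strata. Record the planned status before randomisation and analyse it as planned, not as later received. Keep the plain Wilcoxon as a sensitivity analysis.

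The randomisation strata in 12.5 need not change, so the amendment remains possible during accrual, provided that it is written before any unblinded comparison informs it.

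The cost is one baseline field and one SAP sentence. Three volume bands by two chemotherapy levels make six analysis strata, about 80/6 = 13 patients each on average. Some will be small and contribute little to a van Elteren test; the proportional-odds model with both factors as main effects is less exposed to this. If chemotherapy turns out not to matter, stratifying on it costs under 1 point of power.
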